NCT number: NCT04601532

Official Title: Randomized Controlled Trial Assessing a Novel Glycopolymer Compound in the Treatment of Superficial Partial-Thickness Burns

Study Protocol Document Date: 8/17/2020

TITLE: Randomized controlled trial assessing a novel glycopolymer compound in the treatment of superficial partial-thickness burns.

Abstract: Current effective dressings for burn wounds contain silver (nanoparticulate or ionic), hypochlorite, hydrogen peroxide, sulfa agents, chlorhexidine, iodine or other dilute antiseptics meant to provide some measure of antimicrobial protection. However, all of these materials have some proven limitations in facilitating wound healing and also have notable local and systemic adverse effects. None of the current clinical treatments enhance healing and/or reduce scar formation. The purpose of this study is to test the safety and effectiveness of SynePure™ Wound Cleanser when used in combination with Catasyn™ Advanced Technology Hydrogel for the treatment of superficial partial-thickness burn wounds.

This study is an investigator initiated, single site, University of Pittsburgh, prospective, parallel group, randomized controlled trial comparing SynePure Wound Cleanser and Catasyn Advanced Technology Hydrogel (intervention group) to the current gold standard treatment Silvadene (control group). Both groups will receive the same care other than the treating agent. Subjects will be recruited from the UPMC Mercy Burn Center adult patient pool who have sustained superficial partial-thickness burn wounds that comprise ≤10% of total body surface area (TBSA).

1.0 Objective and Specific Aims:

Primary Objective: To test the effectiveness of SynePure Wound Cleanser when used in combination with Catasyn Advanced Technology Hydrogel for the treatment of superficial partial-thickness burn wounds as compared to standard of care treatment.

Secondary Objective: To test the ongoing safety of SynePure Wound Cleanser when used in combination with Catasyn Advanced Technology Hydrogel for the treatment of superficial partial-thickness burn wounds as compared to standard of care treatment.

Hypothesis: SynePure Wound Cleanser when used in combination with Catasyn Advanced Technology Hydrogel is safe in humans and improves time to heal and infection rates in superficial partial-thickness burn wounds when compared to standard of care treatment.

Specific Aims:

- 1) Compare re-epithelialization rates between treatment groups.
- 2) Compare rates of infection, complication and progression of the wound to deep partial/full thickness between treatment groups.
- 3) Compare healed wound characteristics, Patient Reported Outcomes and Health-related Quality of Life Outcomes between treatment groups.

2.0 Background and significance:

2.1 Background:

Burn wounds are associated with significant morbidity and mortality as well as Quality of Life impairments for the patient. Burn wounds can be particularly problematic as they can compromise skin integrity potentially allowing microbial invasion and subsequent infection. In fact, thermal destruction of the skin provides an ideal environment for microbial colonization. If left untreated, the infection can spread to a systemic level, further jeopardizing the patient.

Topical management via dressings provide a barrier against microbial infection. The current gold standard for burn wound dressings is silver (nanoparticulate or ionic) and it has shown some efficacy in treating infections but it does not demonstrate an ability to prevent infections and some treatment guidelines even recommend against its use.²⁻³ Although silver dressing is preferred for military use, a retrospective review spanning 10 years of use

in military environments showed that silver was not more effective than other antimicrobial topical treatments⁴ and a meta-analysis with over 2500 surgical patients found silver sulfasalazine was associated with increased infection rates and hospital length-of-stays were two days longer on average.⁵

Other current effective dressings for burn wounds include hypochlorite, hydrogen peroxide, sulfa agents, chlorhexidine, iodine or other dilute antiseptics meant to provide some measure of antimicrobial protection. However, all of these have some proven limitations in facilitating wound healing and also have notable local and systemic adverse effects (see ref 6 for review). Finally, none of the current clinical treatments, have demonstrated evidence of enhanced healing and/or reduced scar formation.

Synedgen has developed SynePure Wound Cleanser and Catasyn Advanced Technology Hydrogel. These products are Food and Drug Administration (FDA) 510(k) cleared wound care medical devices formulated with a novel biocompatible chitosan derivative, poly (acetyl, arginyl) glucosamine. SynePure is optimized for the cleansing and debridement of wounds and thermal injuries, and Catasyn serves as a protective gel dressing. Together, these products reduce inflammation in wounds, aggregate bacteria and disrupt bacterial biofilms, and accelerate healing. SynePure and Catasyn are nontoxic, biocompatible, shelf-stable up to two years, easy to use, and may be used in any care setting from the battlefield to a tertiary hospital.

Synedgen optimized Catasyn's formulation, completed GLP biocompatibility studies, and performed engineering and qualification runs for in-house cGMP manufacturing of the product. Catasyn's constituent glycopolymer preparation was optimized and validated under cGMP. Together with collaborators at the University of Miami, the studies necessary to determine the optimized schedule for the treatment of full-thickness burns were completed. Work done in collaboration with the University of Pittsburgh Medical Center further established the efficacy of SynePure and Catasyn's efficacy in a pig model of infected thermal injury. In this study, using SynePure and Catasyn together twice a day, three days a week demonstrated 4-6 day faster healing of methicillin-resistant Staphylococcus aureus burns through reduced infection, increased epithelialization, and faster wound closure as compared to standard of care (Silvadene). Similar results were observed in partial thickness injury infected with Pseudomonas aeruginosa.

We have also explored SynePure and Catasyn's activity by gene array analysis to better understand the gel's capacity to accelerate healing and control inflammation. Confirmation of SynePure and Catasyn's reduction in wound bacterial colonization was confirmed in both our partial-thickness and full-thickness wound porcine models. All toxicology studies performed to date have shown no toxicity and no adverse events have been observed in multiple animal studies including a variety of animal species and several routes of drug administration.

Significance:

SynePure Wound Cleanser and Catasyn Advanced Technology Hydrogel demonstrates an improvement in healing, scarring, fibrosis, and infection of burn wounds and complex open wounds. Its toxicity profile, ability to remove biofilms, healing, and anti-inflammatory properties make a compelling case for further testing of SynePure Wound Cleanser and Catasyn Advanced Technology Hydrogel as a new agent to facilitate healing and limit scarring in burn wounds.

3.0 Research Design and Methods:

The study is a prospective, parallel group, randomized controlled trial comparing SynePure Wound Cleanser and Catasyn Advanced Technology Hydrogel (intervention group) to the current gold standard treatment Silvadene (control group). Subjects will be randomized 1:1, either to the treatment group or the standard of care (Silvadene) control group.

Prior to the candidate's referral into the study, as part of standard of care in the burn center, the burn wound is debrided and cleansed in the hydrotherapy area, and then assessed to categorize the burn (superficial, partial thickness,).

Procedural Summary:

- 1. After informed consent process is completed, the study investigator examines and screens the participant to confirm the diagnosis of a superficial-partial thickness burn and all other eligibility inclusion/exclusion criteria. Medical history, medical record review with participant report, medication profile collections, vital signs, demographics, physical exam with burn wound and surface area assessments are completed at this time. Upon completion of these assessments' all findings are reviewed and participant eligibility is determined based on study inclusion and exclusion criteria.
- 2. Should participant be deemed eligible to continue in research; randomization is performed to determine group assignment with randomization to either the intervention group (SynePure Wound Cleanser and Catasyn Advanced Technology Hydrogel) or the control group (Silvadene). Prior to application of treatment agent and dressing application, 2D photographs will be taken of the burn area for later evaluation.
- 3. During the Initial treatment visit (Day 0), after randomization, the treatment agent is applied (SynePure Wound Cleanser and Catasyn Advanced Technology Hydrogel or Silvadene) to complete secondary dressing with a dry gauze and Kerlix wrap application.
- 4. Patient education on wound care and daily dressing change per routine care. Dressing to be changed daily by patient or provider. Education also provided as to the treatment agent to be applied daily with the dressing change (SynePure Wound Cleanser and Catasyn Advanced Technology Hydrogel or Silvadene).
- 5. Participants will be asked to complete Subject report questionnaires related to the burn wound, symptoms experienced and effects of injury on their activities of daily living.
- 6. The research coordinator will call the participant twice at timepoint Day 1 and Day 3 to assess participant safety, complications/adverse events and address any questions or concerns that the participant may have encountered.
- 7. Follow-up Visits (Visits 2-8) will occur in the UPMC Mercy Burn Center and will consist of wound evaluation, brief history and physical assessment, vital signs, recording of status change since last visit/interaction, medication review, and adverse event collection. 2D photographs will be obtained of burn wound area at time of physical assessment and Subject report questionnaires and wound dressing assessment /treatment agent application (if wound has not yet healed). Reference to the Schedule of Events included with Protocol for additional detail of study procedures.

Recruitment:

Subjects presenting to the study site for treatment of superficial partial thickness burns will be considered for enrollment. Physicians and licensed clinicians within the burn center area, familiar with the study's inclusion/exclusion criteria will assess for potential patients as they arrive to the

Burn Center Clinic for treatment, a part of their burn practice. If the patient is an appropriate candidate and willing to be considered for the study, he/she will be referred to the research team.

After informed consent has been obtained, the study investigators will conduct screening procedures to determine study eligibility. Should the participant meet criteria, he/she will proceed to randomization on Day 0 prior to treatment application. Enrolled subjects will be randomly assigned per a predefined 1:1 randomization scheme to either the interventional group or control group.

Active Treatment:

During the initial treatment visit (Day 0), the wound will undergo hydrotherapy debridement per routine care and at which time 2D photographs of the wounds will be obtained prior to randomization. Participants assigned to each group will have their treatment applied per their randomization status, either SynePure Wound Cleanser and Catasyn Advanced Technology Hydrogel (intervention group) or Silvadene (control group). They also will be given written instructions on how to apply the treatment at home and a sufficient supply to last until their next visit.

Consent and Screening procedures:

All screening procedures will be performed at the UPMC Mercy burn center in a private room after this informed consent document is signed. These screening procedures will take approximately 2-3 hours.

- Informed consent
- Review of medical records related to the injury, past surgeries, and general health events
- Demographic information and allergy collection
- Physical assessment inclusive of an evaluation to your burn wound area
- Medication collection
- Vital sign measurement (such as temperature, heart rate, blood pressure and respiration rate) collection
- Pregnancy Test (Urine Dip)

Initial Treatment Visit 1 (Day 0):

After all screening procedures have been completed and reviewed by the investigators and eligibility will be determined. Should the participant be determined to be eligible to continue participation, the initial treatment procedures will be continued and all procedures may occur on the same day as the screening visit. This visit will be performed at the UPMC Mercy Burn Center. The total length of time for this visit will take approximately 2-3 hours of time.

- Randomization process with assignment to 1 of 2 treatment groups where either SynePure Wound Cleanser with Catasyn Advanced Technology Wound Hydrogel OR Silvadene will be applied. Both groups will then receive a secondary dry dressing covering consisting of gauze and Kerlix wrap.
- 2D photographs will be obtained focusing on the burn injury area, prior to the wound being dressed.
- Written instructions will be provided describing how to apply the wound treatment and
 dressings daily in between to the participant. Should the participant be in hospital
 during the healing of the burn wound these daily dressings will be performed by either a
 member of the clinical staff or the research team.

- Completion of Subject Self-report questionnaires that pertain to the burn wound, pain, and other symptoms that experience. Potential effects and relationship to the participant's quality of life and activities of daily living
- Adverse events collection

After this initial visit, the research team will reach out to the participant by phone on Day 1 and Day 3 of the study schema to determine if there are any questions, issues or concerns that the participant may be experiencing. Additionally, they will remind and confirm the next in person visit to the clinic.

Follow-up Visits (Visits 2-8):

These Visits will occur in the UPMC Mercy Burn Center and have a duration of 1-2 hours to complete. These visits will consist of wound evaluation to assess for healing, brief history and physical assessment, vital signs, recording of status change since last visit/interaction, medication review, and adverse event collection. 2D photographs will be obtained of burn wound area at time of physical assessment and prior to wound dressing /treatment agent application (if wound has not yet healed) and subject report questionnaires consisting of SF-12, Wound Experience and Satisfaction questionnaires, Vancouver Scar Scale, POSAS Questionnaires (described in the following section). During the study visit, continued instructions for at home dressing and treatment application will be reinforced.

Subject Reported Questionnaires:

Vancouver Scar Scale Score: The VSS⁹ is a scale to assess the extent of scarring for a given wound by scoring the pigmentation, vascularity, pliability and height of the scar. Each domain is individually scored then the domains are summed to give a total score that range from zero (0) to 13 with zero (0) representing a 'normal' presentation. Validity and reliability of the scale have been documented 10-12 and is commonly used in wound healing research.

SF-12: The SF-12¹³, an abbreviated version of the SF-36, is a patient self-reported twelve questions survey of general health, physical functioning, role functioning (physical and emotional), bodily pain, vitality, mental health, and social functioning. The scale is comprised of two scores: physical component summary (PCS) and mental component summary (MCS). Scores are summarized and normalized. While the survey demonstrates moderate validity and reliability, ¹⁴ the survey is ideal for use as it is brief and commonly used, so comparisons between studies are possible.

POSAS: The patient and observer scar assessment scale¹⁵⁻¹⁶ is used to measure scar quality. It is composed of a patient reported section and an observer reported section. Each section consists of six items that are scored numerically on a ten-step scale. These are then summed together to make up the total score. There is also an overall opinion section for both the patient and the observer. While validity and reliability are marginal for the POSAS, scores have shown little variance from the gold standard, the Vancouver Scar Scale, and it has the distinct advantage of incorporating the patient's perspective.

Wound Experience Questionnaire: The wound experience questionnaire ¹⁷ consists of three sections regarding the patient's wound. The questionnaire is used for wounds early into the healing process and wounds that have dressings. This has been primary used in patients with surgical wounds but can be adapted to wounds not specifically operative, such as burns. Validity and reliability evidence have not been published but the questionnaire has the unique capability to assess a primary focus of this study. In addition to assessing patient satisfaction with the healing process, the questionnaire also assesses patient satisfaction with the wound dressings as distinct categories.

3.1 Data Collection and Statistical Consideration:

Sample Size Estimation:

In this study, the minimal median difference of three (3) days to healing is determined to be the clinically relevant difference. Given an assumed median time of 15 days to healing for the Silvadene comparator group 18 , a corresponding hazard ratio of 0.8 for the intervention group is anticipated. a sample of 45 in each group (90 total) is required to detect a statistically significant difference [confidence level ($\alpha \leq 0.05) - 95\%$; Power - 80%]. Assuming a 10% attrition, it is recommended to enroll up to 100 subjects to achieve a sample of 90 subjects. This will be easily accomplished in our outpatient burn clinic, with a 400-patient annual volume, and we will use a 3-week evaluation period so that the trial can be accomplished in a year.

Analytic Plan:

Descriptive statistics will be presented as means and standard deviations for continuous data and as counts and percentages for dichotomous and categorical data. Time-to-event curves with Kaplan-Meier (KM) estimates will be used to compare overall median time to wound healing between treatment groups. Comparison of KM curves will be performed using the log rank test as the curve is assumed to be non-parametric or semi-parametric, and the baseline hazard is not related to the group assignment. Relevant clinical and demographic variables may be assessed for their independent contribution in time-to-event outcome using univariate screening and the hazard is assumed to be relatively constant across the study window. Multiple regression modeling (Cox Proportional Modeling) and adjusted KM curves will be assessed as appropriate. Variables will be included in the multivariate analysis if the univariate screening p-value is < 0.10 and multivariate parameters will be presented as hazard ratios with their corresponding 95% confidence intervals.

Infection, complication, and progression rates will be compared using the Chi-squared test or the Fisher exact test if the data is very unequally distributed within the contingency table, which is anticipated for infection rates. Repeated Measure Analysis of Variance (ANOVAs) will be performed to assess differences in PROs with the days since wounding as the Within-Subjects factor and treatment groups as the Between-Subjects factors. Bonferroni post-hoc analyses may be performed for all statistically significant main effects. Baseline demographic and clinical characteristics will be compared between treatment groups with Independent samples t-test for continuous data and Chi-squared test for dichotomous and categorical data.

Analysis will be performed using SPSS (IBM SPSS Statistics for Windows, Version 25.0. Armonk, NY: IBM Corp.) and statistical significance will be determined at $p \le 0.05$ with the exception of univariate screening as previously described.

Outcome definitions:

- 1. Healed wound: 90% reepithelialization (skin and mucous membrane replacement) of the wounded area.
- 2. Infection: characterized by local new inflammation, heat, purulence as well as new or increased pain, redness and swelling
- 3. Complications other than infection: gangrene, necrosis, periwound dermatisis and/or edema, hematoma, or any other complication determined to be related to the wound and/or treatment

4. Progression; recategorization of the wound to a more advanced state deep partial thickness, full thickness. Failure to heal with 21 days of injury also may be determined as progression by the investigator.

4.0 Human Subjects:

4.1 General Characteristics:

Inclusion criteria:

- 18 years of age or older, Male and Female
- Ability to provide informed consent
- Patients who have sustained superficial, partial thickness burn wounds ≤ to10% of total body surface area (TBSA)
- Patients otherwise in good general physical and mental health, as per the investigator's clinical judgment

Exclusion criteria:

- Inability to provide informed consent
- Deep partial-thickness burns and full-thickness burns
- Radiation, chemical or electrical burn injury
- Patients with burns primarily located to the face, genitals, or span across joints
- Patients whose burn injury was ≥ to 48 hours prior to entry into the UPMC Mercy Burn Clinic.
- Patients with uncontrolled cerebrovascular disease, cardiovascular disease, concurrent endocrine, hepatic or renal disease, or other severe conditions for whom, in the investigators' discretion would render study participation unsafe
- Current pregnancy
- Patients with concurrent burn related injuries or inhalation injury that would put the patient at increased risk, per physician discretion
- Any condition to which in the investigator's discretion would render study enrollment a safety concern for the patient.

All patients who present to the UPMC Mercy ER or Burn Center, whose burns are assessed to be superficial, partial thickness burns, and who also meet the study's eligibility criteria in the opinion of the referring physician will be considered for participation.

The racial, gender and ethnic characteristics of the proposed subject population reflects the demographics of Pittsburgh and the surrounding area and/or the patient population of the University of Pittsburgh Medical Center. We shall attempt to recruit subjects in respective proportion to these demographics. No exclusion criteria shall be based on race, ethnicity, gender, or HIV status.

The study will plan to enroll 115 subjects in order to randomize 100 subjects, to either the intervention group (SynePure Wound Cleanser and Catasyn Advanced Technology Hydrogel) or the control group (Silvadene). It is expected that some subjects will not meet screening criteria after they are consented, and will therefore not proceed forward to randomization.

4.4 Recruitment Procedures:

Subjects presenting at the UPMC Mercy burn center (whether initially seen at the Mercy Emergency Center, or at the outpatient burn clinic) for the treatment of burn wounds will be considered for enrollment. The potential candidate while in the hydrotherapy area, where

as standard of care, the burn wounds are debrided and assessed for depth classification will be introduced to the study. Appropriate candidates will be introduced by the treating physicians and clinical team to the research and will determine interest from the potential candidate in the research. If interest is expressed, the potential candidate will be introduced to the study team and the informed consent process will be initiated, should the candidate express willingness to proceed. Informed consent will be performed prior to any screening or intervention procedures.

The study investigator along with the research coordinator will discuss with the subject the nature of the research study, design schema, the risks and benefits, cost and payments and rights as a research subject participant. The potential subject will be provided with ample time to review the informed consent document and ask questions. Should the potential subject wish to take additional time to review the consent or discuss it with his/her family, or medical personnel he/she will be able to. The study investigator will provide the potential subject a private area within the burn center to conduct this informed consent document review prior to signing the informed consent.

Technical terms will be described using lay terminology and subjects will be permitted and encouraged to ask questions, and all will be answered to their satisfaction. In addition to the consent, the study schema lists the elements of each visit's requirements for participation in a visual and accessible way. Study investigators, or their clinical designee, will be responsible for obtaining informed consent and signing the informed consent document.

4.5 Risk/ Benefit Ratio:

As part of this study's goals are assessing the safety of the intervention treatment in patients with superficial partial-thickness burns, not all possible risks and adverse effects are known.

Risks associated with SynePure Wound Cleanser and Catasyn Advanced Technology Hydrogel include:

SynePure Wound Cleanser

Has been approved for external use in cleaning dermal wounds (including superficial partial-thickness burn wounds).

• There were no adverse events found upon topical application.

Catasyn Advanced Technology Hydrogel

Has also been approved for external use for dressing of wounds (including superficial and superficial partial-thickness burn wounds).

• There is a low risk of redness where the hydrogel is placed on the skin.

Risks associated with Silvadene include:

- Dermatologic
 - Skin discoloration
 - Burning sensation
 - o Itching
 - o Rashes
 - Skin photosensitivity (sensitivity to sunlight)
 - Skin necrosis (death of skin)
- Gastrointestinal reactions/ upset stomach

- Renal
 - o Interstitial nephritis (inflamed kidneys)
- Hepatic
 - Hepatitis (inflamed liver)

Uncommon risks associated with Silvadene include:

- A small risk of adverse reaction associated with systemic absorption (This may lead to deposition of silver in your organs.
- Blood disorders
 - Agranulocytosis- dangerously low level of white blood cells, leading to immunocompromise
 - o Aplastic anemia- body stops producing enough new blood cells
 - o Thrombocytopenia- decreased platelet count
 - o Leukopenia- decreased neutrophil count
 - o Hemolytic anemia- destruction of red blood cells faster than they are produced
- Dermatologic and allergic reactions
 - Stevens-Johnson syndrome (SJS)
 - Toxic epidermal lysis (TEN)
 - o Exfoliative dermatitis
- · Hepatocellular necrosis
- CNS reactions
- Toxic nephrosis

Additional risks associated with the study protocol include:

- A breach of confidentiality.
- Distress or anxiety associated with completing the questionnaires

There is no known direct benefit to the study participants. There may be direct benefit due to an additional period of monitoring and therapy beyond typical standard of care. While there is no guarantee or benefit from this research, demonstrating safety and preliminary efficacy of these devices could provide a new approach in partial thickness burn treatment and could prevent decreased function and disability in civilian and military trauma.

5.0 Costs and Payments:

Costs: The study treatments (SynePure and Catasyn, and Silvadine) and will be provided by the manufacturer for this study, and research procedures will be completed at no cost to the participants. However, all standard of care procedures (i.e. recommended labs or scans) and costs associated with burn treatment visits will be charged to the participant's insurance, and they will be responsible for all associated test or visit co-pays as well.

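### The safety part of the hypothesis has only tests of difference behind it in the analytic plan; at about 45 per arm a non-significant result cannot support it, and no interval for the excess risk is planned

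*Combined protocol and SAP*

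**What the plan says.** Section 1.0 states the aim as "Secondary Objective: To test the ongoing safety of SynePure Wound Cleanser when used in combination with Catasyn Advanced Technology Hydrogel", compared with standard of care. The hypothesis in the same section has two parts: that "SynePure Wound Cleanser when used in combination with Catasyn Advanced Technology Hydrogel is safe in humans", and that it improves time to healing and infection rates. Specific Aim 2 is to "Compare rates of infection, complication and progression of the wound to deep partial/full thickness between treatment groups". No acceptable excess, margin or target rate is attached to any of these.

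The Analytic Plan in section 3.1 states: "Infection, complication, and progression rates will be compared using the Chi-squared test or the Fisher exact test", with Fisher for very uneven tables, "which is anticipated for infection rates". The threshold is 0.05. Confidence intervals appear once, for the Cox model of time to healing: "multivariate parameters will be presented as hazard ratios with their corresponding 95% confidence intervals". Adverse events are collected on Day 0, in the Day 1 and Day 3 calls and at Visits 2-8 (section 3.0). The Analytic Plan names no comparison of them beyond its general provision for counts and percentages.

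Under Sample Size Estimation, "a sample of 45 in each group (90 total) is required to detect a statistically significant difference" refers to time to healing. No sample size, power or expected event rate is given for a safety outcome.

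**The concern.** A test of difference can show that two rates differ. Failing to reject does not show that they are similar, and it is the likely outcome in a small trial with uncommon events even when one arm is worse. The safety part of the hypothesis is a claim that harm is absent or acceptable, so the planned test cannot deliver it. The result that would show how much excess harm remains possible, an interval for the rate difference, is not planned.

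At stake is the wording of the safety conclusion. With no other criterion written down, a report could slide from no significant difference to safe while a clinically important excess of complications or progression had not been ruled out.

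**Working it through.** **The plan's own figure.** There is no safety calculation to reproduce. The 45 per group comes from time to healing (hazard ratio 0.8, 5% level, 80% power). The attrition step reproduces: 90/0.9 = 100. The 90 does not: Schoenfeld's formula gives 4 × (1.960 + 0.842)² / (ln 0.8)² = 631 events. That is a separate matter; here 45 per arm is taken as the planned analysed size.

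**Inputs.** n = 45 per arm (section 3.1). Level 0.05 (section 3.1); sidedness is not stated and is taken as two-sided. Event rates are not in the documents. Those below are assumptions, with control rates from 2% to 20%.

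**Power of the planned test.** For every pair of counts (a control, b intervention) out of 45, compute the two-sided Fisher p. Then sum the product of the two binomial probabilities over pairs with p ≤ 0.05 and b > a.

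| Control v intervention (assumed) | Fisher power |
|---|---|
| 2% v 4% | 0.4% |
| 5% v 10% | 6% |
| 5% v 15% | 23% |
| 5% v 20% | 48% |
| 10% v 20% | 18% |
| 20% v 40% | 46% |

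An excess of about 20, 23, 27 or 30 points is needed for 80% power at control rates of 2%, 5%, 10% or 20%. The normal approximation to the Chi-squared test gives 14% for 5% v 10% and 35% for 5% v 15%, which is still low.

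**What a non-significant result leaves open.** Newcombe's 95% interval for d = intervention minus control combines the Wilson limits (l, u) of each rate. The upper limit is d + √[(u_I − p_I)² + (p_C − l_C)²], and the lower limit mirrors it.

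- 3/45 v 3/45: p = 1.0. Each rate is 0.0667 with Wilson limits 0.0229 and 0.1786. The half-width is √(0.1119² + 0.0437²) = 0.120, so the interval is −12 to +12 points.
- 5/45 intervention v 2/45 control: Fisher p = 0.43, d = 6.7 points. The upper limit is 0.0667 + √(0.1239² + 0.0322²) = 0.195, so the interval is −5.5 to +19.5 points.
- 5/45 intervention v 0/45 control: Fisher p = 0.056, d = 11.1 points, interval about +1 to +23.5 points. The test is not significant although the interval lies wholly on the side of harm.
- No events in 45 in one arm: the one-sided 95% upper limit is 1 − 0.05^(1/45) = 6.4%.

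**Size of a formal alternative.** For a non-inferiority test with equal true rates p, margin m, one-sided 0.025 and 80% power, n per arm = 2p(1 − p)(1.960 + 0.842)²/m². For an illustrative m of 10 points this gives 75, 142 and 252 per arm at p = 5%, 10% and 20%. At 45 per arm the power is about 59%, 35% and 22%. Both margin and rates are assumed.

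**The case against.** A reader might infer that the trial intends to declare the product safe if p > 0.05. The documents do not support that. Nothing says non-significance will be read as safety, Aim 2 asks only for a comparison of rates, and section 4.5 admits that not all risks are known. What stands is narrower: the hypothesis asserts safety, and the Analytic Plan gives no other criterion for it.

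A reader might also infer that Chi-squared and Fisher tests are wrong for these outcomes. For infection they are right, because the hypothesis claims an improvement there. Progression may include failure to heal within 21 days, so it too is partly an efficacy outcome.

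Other points limit the weight:

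- The text between section 5.0 and the references was not available for review and may contain safety monitoring or reporting. The statement about missing methods therefore covers only the available text.
- Counts and percentages are planned, so a reader of the results could compute the intervals. That does not settle in advance how the conclusion will be worded.
- The protocol describes both products as 510(k) cleared, and safety is a secondary objective. This lowers the priority but does not answer the plan's own comparative question.
- If all 100 randomized subjects contributed safety data, Fisher power at 50 per arm, by the same enumeration, would be 6%, 24% and 51% for 5% v 10%, 15% and 20%, so little changes.
- Interval reporting does not define what counts as safe either. That is correct: it states the remaining uncertainty and is no substitute for a margin test.

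**Conclusion.** The point holds in a limited form. In the available analytic plan, the safety objective and the safety part of the hypothesis have no inferential method except tests of difference on infection, complication and progression. Rate differences have no planned interval, and adverse events have no specified between-group analysis. A non-significant result from those tests cannot support the safety claim: even a fourfold rate (5% v 20%) would be missed about half the time, and identical observed counts of 3 per arm leave an excess of up to 12 points possible. These sizes rest on 45 per arm, a two-sided 0.05 level and assumed event rates, since the documents give none. The logical point does not depend on the rates. This is an inexpensive improvement of lower priority and does not affect the healing analysis or the test of infection superiority.

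**What to change.** In section 3.1:

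1. Keep the Chi-squared or Fisher test for the claim that infection rates improve.
2. For the safety objective, report the risk difference (intervention minus control) with a 95% Newcombe or Miettinen-Nurminen interval for complications, progression and adverse events, and for infection as well.
3. Word the safety conclusion as the largest excess risk that the upper limit excludes, rather than as a statement that the product is safe.
4. State that p > 0.05 will not be taken as evidence of safety, and that these intervals describe uncertainty and are not a formal non-inferiority test.

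The cost is a few sentences and some extra table columns, settled before results are seen. No new data, larger sample or change in care is needed. The downside is a more modest safety statement.
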